Specific Aim 1: The first specific aim is to demonstrate that spatial abilities are malleable in persons with DS. Uttal et al. (2013) conducted a meta-analysis on more than 200 spatial intervention studies in individuals of all ages demonstrating that abilities are highly malleable and that even limited experience in spatial tasks can produce positive and lasting effects in TD children and adults. Indeed, numerous studies have shown that spatial ability performance of TD children and adults can be achieved by providing experience with tasks that utilize spatial abilities and do not require direct instruction (e.g., block play and puzzle construction). It is reasonable to expect that these results will generalize to persons with DS. However, this needs to be empirically evaluated. Hence, one important goal of the proposed research is to demonstrate that experience with spatial tasks can promote improvement in two specific spatial abilities (mental rotation and perspective taking) in persons with DS. To test this specific aim, we will compare spatial ability performance of persons with DS before and after varying levels of experience with spatial activities.

Specific Aim 2: The second specific aim is to evaluate whether persons with DS and TD children matched on nonverbal ability exhibit the same degree of improvement as a function of similar experience with spatial abilities. If persons with DS exhibit greater improvement than TD children, then it may be that the weaknesses observed in spatial abilities reflect a lack of opportunity to engage in spatial ability experience. If, on the other hand, persons with DS exhibit less improvement, it may be that weaknesses observed in spatial abilities reflect a lesser ability to benefit from intentional experiences. In the proposed research, we will also evaluate the relations between degree of improvement and measures of Nonverbal ability, Receptive Language, and Chronological Age to identify differences in how these variables contribute to performance improvements in the two groups. The results of these analyses may also help to identify persons with DS who are most likely to benefit from spatial ability experience to promote improvements in spatial abilities.

c) **Describe the study design (e.g., single/double blind, parallel, crossover, control, experimental, observational, etc.)**

N/A

Single blind

Double blind

Parallel

Crossover

Control group

Experimental group

Observational

Other

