Is University of Alabama acting as a coordinating center for other sites? Y

Will the University of Alabama site be participating in all parts/procedures/arms of the study? Y

If No, explain what University of Alabama will NOT participate in:

b) Describe all the procedures, from screening through end-of-study, that the human participant must undergo in the research project, including study visits, drug treatments, randomization and the procedures that are part of standard of care. Specify which procedures are for research and which are standard of care. If study involves only retrospective record review, describe that review process here, including how records will be selected for review. Please note: The box below is for text only. If you would like to add tables, charts, etc., Click "Add" to attach the documents.

The initial assessment will include four measures:

Ravens 2 Matrices: The Ravens 2 Matrices is a 60 item measure of nonverbal ability. The subtest measures a participant's ability to solve problems, identify relationships, and complete visual analogies without testing language skill. The examiner shows the participant pictures or abstract designs that follow a pattern, with one element missing. The participant is instructed to point to a picture that will complete the pattern. Participants will be matched on raw score performance. Completing the subtest should take less than 15 minutes for most participants.

PPVT-4: The PPVT – 4 is a norm-referenced test for measuring receptive vocabulary of children and adults. The test is administered individually. Each item consists of four colored pictures that serve as response choices on each page. For each item, the examiner says a word and the examinee selects the picture option that best represents the word's meaning. The test is normed for 2 years, 6 months to 90 years. Average time to administer the test is 10 – 15 minutes.

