c) Provide stopping rules for the study. If the proposed study is a clinical trial where a drug, vaccine, device or other treatment is compared to a placebo group or comparison treatment group, what are the guidelines or endpoints by which early decisions regarding efficacy or lack of efficacy can be made? For example, it may be reasonable to stop enrollment on a study when efficacy has already been clearly demonstrated, to avoid unnecessary enrollments of additional participants. Alternatively, it may be reasonable to stop enrollment when it is clear that efficacy will never be demonstrated, given the statistical power of the study as designed. Describe the guidelines that are in place to assist in making these determinations, if relevant to the proposed study.

NA

d) Describe how data analysis will be performed (statistical tests, methods of evaluating data) and indicate the smallest group/unit for which separate reporting will occur. For studies involving a questionnaire, if data and reliability information are available, please describe or provide references. (Page numbers from a sponsor's protocol/grant may be referenced in this section).

The independent variables of interest will be Group (DS and TD), Delay (No Delay and Delay), and Assessment (1, 2, and 3). The smallest number of participants in any given cell of the design is 20 participants.

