*** * * Subject Population(a-h) * * ***

7. Subject Population - In the space below, please detail the participants that you are requesting to recruit (include description of each group requested)

a) Expected age range of participants. (For example - 19 yrs to 90 yrs).

Participants with Down syndrome will be between 10 and 30 years of age.

Typically developing children will be between 4 and 9 years of age.

We will test 48 participants per group - plus an additional 6 typically developing children as needed to provide a closer match on nonverbal ability for the children in the Experimental condition with the children in the control condition.

b) i) Number to be directly solicited for this research.
 
ii) Number to be consented (including withdrawals or screen failures)
 
iii) Number expected to complete the study.
 
c) If this is multi-center study, number of participants to complete the study study-wide
 
d) If study involves review of medical or other records, number of records to be reviewed.
 
e) If women, minorities, or minors are excluded, a clear compelling rationale must be provided unless not applicable. Examples for not including minors: disease does not occur in children; drug or device would interfere with normal growth and development; etc.
 
f) Describe how potential participants will be identified for recruitment (e.g., chart review, referral from individual's treating physician, those individuals answering an ad). How will potential participants learn about the research, and how will they be recruited (e.g., flyer, e-mail, web posting, telephone, etc.)? State where recruitment materials will be located. Click "Add" to upload recruitment materials document.
	
X N/A
 
N/A
 
102
 
102
 
N/A
 
102
 
X N/A
 
NA

--	--

Important to remember: Study Activities cannot begin until IRB approval is granted.

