The children used in this study are necessary for providing a comparison group matched on non-verbal ability with participants with Down syndrome. In this type of research, it is necessary to evaluate the performance of individuals with Down syndrome against participants who are matched on general ability measures to determine if the difficulties associated with Down syndrome are beyond that which would be expected based on developmental level.

b) Has this research been conducted in adults? Y

If yes, is there any indication that the proposed research would benefit, or at least not be harmful to children?

Similar research has been conducted in adults and children with no adverse effects. The children are essential for providing a comparison group for the participants with Down syndrome.

c) Indicate how many children you propose to enroll in the study and justify this number (whenever possible, involve the fewest number of children necessary to obtain statistically significant data which will contribute to a meaningful analysis relative to the purpose of the study).

All of the typically developing participants will be children (48 participants originally planned). Many of the participants with Down syndrome will also be participants (we anticipate about half of the 48 participants in this group, or 24). The total number of participants was determined by power analysis. A 4 groups x 3 repetitions analysis with alpha set at .05, power set at .80, and total N = 96 (24 in each group) would be sufficient to observe a significant effect size (f(V)) of .27 or greater. To evaluate the power for simple effects tests to compare the effects of training for the DS and TD participants separately, we conducted a 2 groups (Delay and No Delay) x 3 repetitions analysis with alpha set at .05, power set at .80, and total N = 48 (24 in each group). Power analysis indicated that 48 total participants would be sufficient to observe a significant effect for effect sizes (f(V)) of .27 or greater for main effects of Delay and of .25 or greater for main effects of Assessment Time. Power calculations were conducted in GPower 3.1.9.2 (Faul et al., 2007). However, we are requesting an additional 6 typically developing participants at this time to make it possible to better match the Experimental and Control group children on nonverbal ability.

d) Describe how assent of a child will be obtained and documented (if applicable). If not applicable, explain why.

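### No age is eligible in both groups (4 to 9 v 10 to 30 years), so a Down syndrome v typically developing difference in how age relates to improvement could not be attributed to Down syndrome

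*Combined protocol and SAP*

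**What the plan says.** Item 2(b), Specific Aim 2, adds a predictor analysis to the comparison of improvement between groups: "we will also evaluate the relations between degree of improvement and measures of Nonverbal ability, Receptive Language, and Chronological Age". Its stated purpose is "to identify differences in how these variables contribute to performance improvements in the two groups". The sentence after it gives a second use, finding which persons with DS stand to gain most.

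Item 7(a), Subject Population(a-h), fixes the ages: "Participants with Down syndrome will be between 10 and 30 years of age" and "Typically developing children will be between 4 and 9 years of age".

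Matching is on nonverbal level. Under the matrices measure in item 3(b): "Participants will be matched on raw score performance". Subject Population(m), Section 2(a), gives the reason for the TD group: "The children used in this study are necessary for providing a comparison group matched on non-verbal ability with participants with Down syndrome". There is no comparison group of the same chronological age as the DS group.

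The analysis description in item 3(d) names three factors: diagnosis group, delay condition and assessment occasion. It contains no model for the age relation, no functional form for age, and no limit on how a differing age relation will be read.

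**The concern.** For nonverbal ability the groups are matched, and for receptive language they can share a range of scores. Asking whether such a variable works differently in the two groups is then a comparison of like with like over the shared scores. For age it is not. Every eligible TD child is younger than every eligible participant with DS, so the comparison sets early childhood in one group against late childhood to adulthood in the other.

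If benefit from spatial experience changes with age along a curve, for example rising in childhood and then flattening, two groups observed on different stretches of that one curve will show different age relations even though Down syndrome plays no part. The difference could then be reported under Aim 2 as a feature of Down syndrome. A larger sample would not help, because the gap comes from eligibility and not from imprecision.

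**Working it through.** **The plan's own figure.** The documents give no figure for the age analysis. The main sample-size statement (Subject Population(m), Section 2(c): 4 groups x 3 repetitions, N = 96, alpha .05, power .80, f(V) = .27) does reproduce. With df 6 and 184 and noncentrality 0.27² x 96 x 2 = 14.0, power is 0.797, and the effect detectable at 80% power is 0.271. The point does not depend on it.

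**Step 1: common support.** Reading each range as generously as possible, TD covers 4 to just under 10 and DS covers 10 to just under 31 (item 7(a)). The overlap is zero. This needs no assumption.

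**Step 2: what a Group x Age test does when nothing differs.** The model is improvement = b0 + b1 Group + b2 Age + b3 (Group x Age) + error, testing b3 = 0 at a nominal 5%.

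Inputs from the documents:
- age ranges from item 7(a);
- planned size (item 7(a)): "We will test 48 participants per group - plus an additional 6 typically developing children", run as 48 and 48;
- consented to date (Continuing Review form, item 5): 54 TD and 30 DS.

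Assumptions, not in the documents:
- ages uniform within each range;
- residual SD of improvement 1;
- one age curve common to both groups, with no effect of Down syndrome;
- 4,000 simulated trials per row.

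| Common age curve | Fitted slope per year, TD / DS | Rejects, 48/48 | Rejects, 54/30 |
|---|---|---|---|
| Linear, 0.1 SD per year | 0.10 / 0.10 | 4.6% | 5.0% |
| log(age) | 0.15 / 0.05 | 19% | 19% |
| 2 x log(age) | 0.30 / 0.10 | 59% | 61% |
| 0.15 SD per year, flat from age 10 | 0.15 / 0.00 | 38% | 41% |
| 0.30 SD per year, flat from age 10 | 0.30 / 0.00 | 92% | 93% |

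**Step 3: hand check of one row** (0.15 SD per year, flat from 10; 54/30). The variance of a uniform age is span²/12, giving 6²/12 = 3.0 for TD and 21²/12 = 36.75 for DS. The SE of the slope difference is √[1/(54 x 3.0) + 1/(30 x 36.75)] = √(0.00617 + 0.00091) = 0.084. Then z = 0.15/0.084 = 1.78, and the chance of exceeding 1.96 is about P(Z > 0.18) = 43%. The simulated 41% agrees, allowing for ages that vary from sample to sample.

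**Step 4: can the trial's data rescue the comparison?** The error rate stays at 5% when the common relation is a straight line from 4 to 30. A bend between the TD and DS ranges, and a difference between the groups, predict the same data. With no age observed in both groups, the two cannot be told apart.

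**The case against.** **The age gap is deliberate.** Matching on nonverbal level makes the TD group much younger, and the main DS v TD comparison needs that matching. This stands. The point is not a criticism of the matching, only of carrying age into a between-group comparison that the matching rules out.

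**The affected item is small.** It is one of three variables in an additional analysis that item 3(d) does not take up. The stated use for identifying who benefits most relies on the relation within DS, which can still be estimated. This also stands, and it sets the weight of the point.

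**Aim 2 does not say that an age difference would be put down to Down syndrome.** True. Its interpretive sentences, on lack of opportunity against lesser ability to benefit, concern overall improvement. But the aim of identifying between-group differences in the role of age is explicit, and nothing limits how such a difference would be read.

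Three stronger readings are tempting, and the documents do not support them:

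- *The analysis is bound to return a spurious difference.* It is not. Under a linear relation the test holds its 5% level, and the other rates depend on the assumed curve.
- *The unequal widths of the age ranges are themselves the flaw, because equal correlations imply different slopes per year.* In that case the slopes do differ, so rejecting equality is correct. The same would happen with overlapping ranges of unequal width. Nor does the plan say that slopes will be compared; it speaks only of relations and contributions.
- *Age will distort the whole-sample Aim 2 model, or the lay summary repeats the problem.* Item 3(d) plans no age covariate. The lay summary (item 2(a)) asks only whether age is associated with benefit and makes no comparison between groups.

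**Conclusion.** The concern holds as a limit on interpretation. Aim 2 plans a between-group comparison of the role of chronological age that the eligible ages cannot support: a difference, if seen, could not be attributed to Down syndrome rather than to stage of life.

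The absence of overlap is a fact of the documents. Its consequence for error rates is illustrative only, from about 5% to over 90% across the curves tried. Those figures rest on the assumed uniform ages, residual SD and curve shapes, and are not a prediction for this trial.

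A reader might infer that Aim 2 as a whole is compromised. It is not. The age relation within DS, the matching on nonverbal ability, the Delay v No Delay contrasts and the Assessment x Group test are all unaffected. This is a cheap improvement to a secondary analysis.

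**What to change.** Revise the predictor sentence in item 2(b), Specific Aim 2, so that it does three things:

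1. Keeps the between-group comparison of contributions for nonverbal ability and receptive language, restricted to the range of scores that both groups share.
2. Reports the chronological age relation within each group only, for that group's own range (4 to 9 for TD, 10 to 30 for DS), and labels it exploratory.
3. States that no DS v TD conclusion about age will be drawn, because no age is represented in both groups.

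The Continuing Review form (item 13) says data collection is complete and analysis is underway, so this can still be settled before reporting. If the age relations have already been compared, the same limit belongs beside the result.

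The cost is a wording change and the loss of one secondary between-group comparison. No data, recruitment or main test is affected.

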Based on available literature and our own preliminary research, we have concluded that persons with Down syndrome (DS) exhibit difficulties in utilizing the specific spatial abilities of mental rotation and perspective taking, and performing complex spatial tasks such as wayfinding and environmental learning. A weakness in spatial abilities may have many direct applications to daily life, ranging from activities such as tying shoes to using hand tools and navigating the environment. They also serve as a cognitive foundation for many other complex skills such as solving mathematical problems and using spatial language for giving and receiving directions. Moreover, they are used in a variety of specialty jobs such as grocery stocking, packaging, and assembling, which are among the most commonly reported jobs for adults with DS. Hence, a new focus on spatial ability and its modifiability in persons with DS is clearly warranted. The primary goal of the research proposed in this application is to evaluate the malleability of mental rotation and perspective taking in people with DS through providing intentional experience with numerous spatial activities. Two groups of participants will be tested over the course of the project: adolescents and young adults with DS and typically developing children. Following an initial evaluation of performance on the two abilities, participants will receive up to eight sessions of spatial activity experience utilizing puzzle construction, block building, and computer search tasks. Following the experience sessions they will be re-evaluated. These data will be used to investigate two specific aims. First, we investigate whether spatial abilities of persons with DS can be modified by experience with spatial activities. Second, we investigate whether the degree of modification observed for persons with DS can reduce performance differences between them and TD children. We also consider whether performance on the PPVT, KBIT matrices, and Chronological Age are associated with any benefits from spatial ability experience. To the best of our knowledge, this is the first study to use experience with spatial activities to improve spatial ability functioning in persons with DS, or persons with intellectual/developmental disabilities in general for that matter.

b) List your research objectives (specific aims & hypotheses of the study).

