Mixed Design (Between/Within Subjects) Pre-test/Post-test Comparison

d) **Provide a timeline for individual participant recruitment and follow-up (analysis for the study is required).**

Participants will be recruited from various sources including the UA Participant Registry, DS Connect (NIH Registry of individuals with Down syndrome interested in research), local schools, and local service providers. Following initial contact by these various sources, participant families will self-identify to receive additional information about the study - including a copy of the Parental Consent. The study will take place over the course of 4 months for each participant. All participants will receive the PPVT, the KBIT 2 Matrices subtest, an assessment of Mental Rotation, and an assessment of Visual Perspective Taking during the first testing session (Approximately 45 minutes). Mental Rotation and Perspective Taking performance will be assessed two additional times for all participants, once following Experience Session 16 and once following Experience Session 32. These two assessments will take approximately 15 minutes. Experience sessions will be provided twice per week, with each session lasting approximately 30 minutes over a period of 16 weeks. Half of each group (No Delay participants) will begin spatial ability experience during a first experience session scheduled approximately one week following the initial assessment. The other half of each group (Delay participants) will not begin the spatial ability experience for the 8 weeks following the first assessment and serve as a control for practice effects on the assessment measures. The Delay participants will receive a second assessment on the Spatial Abilities and begin spatial ability experience during week 9. They will receive the same protocol as the experimental participants following the second assessment (8 weeks experience, ability assessment, 8 weeks experience, ability assessment). The final assessment will come following Experience Session 32 (week 16). Data analysis is planned upon the completion of all data collection during year 03 of the

project period.

e) Will participant be randomized? Y

f) If participants will be given placebo, please justify placebo use, and describe contents of the placebo. Y

NA

3) Study Procedures

a) Is this project a multicenter study (i.e., same project is conducted elsewhere by a different investigator)? Y

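### The plan relates markers to degree of improvement but infers who benefits from the experience; that inference needs an exploratory marker-by-Delay estimate at Assessment 2, which is not specified

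*Combined protocol and SAP*

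**What the plan says.** Section 2(b), Specific Aim 2, states that "we will also evaluate the relations between degree of improvement and measures of Nonverbal ability, Receptive Language, and Chronological Age", in order to find differences in how these variables contribute in the two groups. It then gives the use to be made of the result: "The results of these analyses may also help to identify persons with DS who are most likely to benefit from spatial ability experience". The lay summary in 2(a) puts the same objective in terms of benefit: "We also consider whether performance on the PPVT, KBIT matrices, and Chronological Age are associated with any benefits from spatial ability experience".

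Section 2(d) randomises half of each group to start the experience at once (No Delay) and half to wait 8 weeks (Delay). The waiting participants "serve as a control for practice effects on the assessment measures". They receive the experience after the second assessment.

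The analysis text in 3(d) lists Group, Delay and Assessment as the independent variables. For Aim 1 it names Delay v No Delay at Assessment 2 as a contrast of interest. It contains no marker term, no marker-by-Delay test and no definition of degree of improvement (which interval, which arm). An Aim 2a is named, but no 2b follows.

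Section 7(a) states: "Participants with Down syndrome will be between 10 and 30 years of age". Typically developing (TD) children are 4 to 9.

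**The concern.** What is to be measured is improvement. What is to be inferred is benefit from the experience. These differ. A change score contains gain from repeating the test, regression to the mean from Assessment 1, and whatever the experience adds. A marker can track the first two and be unrelated to the third. Such a marker is prognostic: it says who will score higher next time. A marker of benefit is predictive: the trained v untrained difference must vary with its level.

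The plan recognises practice gain as a threat and randomises a control for it, but uses that control only for the average effect. Comparing marker relations between DS and TD does not replace it, because practice gain may relate to a marker differently in the two groups.

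At stake is a report that, say, a higher nonverbal score marks the persons with DS who should be offered spatial experience, when those participants might have gained as much untrained.

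The age marker has a further limit. With ranges of 10-30 and 4-9 years, the two age slopes cover different developmental spans.

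**Working it through.** **Inputs from the documents.** Alpha .05, power .80, 96 participants in total and 48 in the DS group (Research Involving Children, Section 2(c)); 30 DS participants consented (Continuing Review, item 5); two outcomes, mental rotation and perspective taking; three markers.

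**The plan's own figure.** The documents give no power figure for the marker analysis. The nearest is f(V) = .27 for 4 groups x 3 repetitions with N = 96. Taken as the multivariate within-between interaction: df1 = (4-1)(3-1) = 6; s = min(3, 2) = 2; df2 = 2(96-4-2+2) = 184; noncentrality = s x N x f(V)^2 = 2 x 96 x .0729 = 14.0. Power is 79.7% and the detectable f(V) is 0.271, so the figure reproduces. It concerns the group and time effects and says nothing about markers.

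**Which comparison matches the claim.** The Delay arm is untrained only up to Assessment 2, so this is the last point with a concurrent randomised control. Within DS the matching model is

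A2 = b0 + b1 x A1 + b2 x Delay + b3 x Marker + b4 x (Marker x Delay).

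Here b3 carries the prognostic part and b4 the difference in training effect per unit of marker.

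**Precision of b4.** Assume equal arms, residual SD 1 and marker SD 1. Then SE(b4) = 2/sqrt(N), noncentrality = b4^2 x N/4, and df2 = N-5.

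| DS N | SE(b4) | 95% half-width | Noncentrality for 80% power | Detectable b4 | Power at b4 = 0.5 |
|---|---|---|---|---|---|
| 48 | 0.289 | 2.017 x 0.289 = 0.58 | 8.21 | sqrt(4 x 8.21/48) = 0.83 | 40% |
| 30 | 0.365 | 2.060 x 0.365 = 0.75 | 8.50 | sqrt(4 x 8.50/30) = 1.06 | 26% |

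About 128 DS participants would be needed for 80% power at b4 = 0.5.

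**Multiplicity.** Three markers x two outcomes is six tests. If independent and unadjusted, 1 - .95^6 = 26% familywise; three tests would give 1 - .95^3 = 14%.

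**Illustration of the false signal.** Assumptions, none from the documents: test-retest correlation .7; a constant experience effect of 0.5 true-score SD, so no true effect modification; and a marker that drives retest gain only, with slope 0.2 or 0.4 true-score SD per marker SD. The error variance is .3/.7 = .429, so the noise variance of a change score is .857. The marker-change correlations are .2/sqrt(.04+.857) = .21 and .4/sqrt(.16+.857) = .40. The table gives the share of simulated trials with p < .05, for slopes 0.2 / 0.4.

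| Reading of improvement | N = 48 | N = 30 |
|---|---|---|
| A1 to A2, both arms, arm means removed | 30% / 81% | 19% / 60% |
| A1 to A2, No Delay arm only | 17% / 51% | 11% / 33% |
| A1 to A3, both arms, practice slope doubled by A3 | 81% / 100% | 59% / 98% |
| Marker x Delay at A2 | about 5% | about 5% |

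The first three rows are the power to detect a correlation that was put in, and the last is the nominal level of a test whose null was built in. The table shows that the two analyses answer different questions. It does not estimate how often this trial would mislead.

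**The case against.** The strongest reply is that the documents choose no wrong analysis; they leave this one open. No interval, arm or model is given, Delay is among the listed variables, and the wording is tentative. This stands. A reader might infer that the plan excludes the untrained arm, or will use the markers to select people. Neither is supported: Delay is not mentioned either way here, and no selection step or decision rule exists.

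A reader might also infer that the planned correlation shows retest gain only. That is too strong. It mixes practice, regression to the mean and benefit, and cannot separate them.

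Section 3(d) expects Delay scores at Assessments 1 and 2 not to differ, so practice gain will be looked at. That check concerns the mean; it does not exclude practice gain that varies with a marker.

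The analysis may be set out in the attached grant proposal, since the form allows applicants to refer to grant pages. No such reference is made in 3(d), so this cannot be relied on.

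The interaction test is weak at these numbers. This stands too. It argues for intervals and a modest claim, not for a correlation that answers another question.

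Finally, the age gap follows from matching on nonverbal ability, and describing age relations within a group is legitimate. That is accepted; only a between-group reading of the slopes is at issue.

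**Conclusion.** The concern holds as a mismatch between the stated measure and the stated inference in a secondary objective. Relating markers to improvement cannot by itself identify who benefits, and the plan does not say how its practice control enters. The point rests on the design alone and needs no assumed correlation.

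The false-signal rates are illustrative. A reader might take the highest of them as the expected error rate, but the documents give no marker-gain correlation, and the rates fall to 11-33% (N = 30) and 17-51% (N = 48) if improvement is taken in the No Delay arm alone.

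The appropriate analysis detects only large differences in benefit: 0.83 residual SD per marker SD at 48 DS participants and 1.06 at 30. The second figure assumes that the 30 consented split 15:15 and all contribute Assessment 2. Section 3(d) gives a smallest cell of 20 and the power statement uses 24, so the actual cell counts should be reported. Any responder statement from this trial can be exploratory at most.

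**What to change.** 1. Within each group, for each marker (kept continuous) and each outcome, fit Assessment 2 score on Assessment 1 score, Delay, marker and marker x Delay.
2. Base any statement on who benefits on the marker x Delay estimate and its confidence interval. Label it exploratory, and state the number of tests (3 markers x 2 outcomes in each group).
3. Define degree of improvement (interval and arm), and report its plain correlations with the markers as prognostic only.
4. Describe age relations within each group, with age centred there. Do not read a DS v TD difference in age slopes as a group difference.
5. Reconcile the nonverbal marker. Sections 2(a) and 2(d) name the KBIT matrices, while 3(b) says "The Ravens 2 Matrices is a 60 item measure of nonverbal ability".

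The cost is a few model terms on data already collected; the Continuing Review (item 13) says analysis is underway, so the change should be dated and recorded as made at that stage. The downside is wide intervals, with half-widths of about 0.58 residual SD per marker SD at N = 48 and 0.75 at N = 30. A null interaction must not be reported as equal benefit at all marker levels.
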